11. PROTECTION OF HUMAN SUBJECTS

11.1. Potential benefits of the proposed research to the study subjects and importance of the knowledge to be gained, and risk/benefit ratio

Potential benefits: There are no anticipated direct benefits to the subjects as a result of their participation in this study nor will this be implied when obtaining consent. However, if our hypothesis is correct, subjects in the active medication groups may experience improvements in their functional class and quality of life, although this will not be implied in any way during informed consent or enrollment.

Importance of the knowledge to be gained: If our hypothesis is correct, this study may identify an effective specific intervention to treat mechanistic abnormalities in AS patients. Furthermore, if improving these abnormalities leads to an enhanced exercise capacity in this patient population, this would lead to a new paradigm in the field and a better understanding of the mechanisms that lead or contribute to AS, which will accelerate the discovery of new treatments for this condition. In addition, if potassium nitrate proves effective in enhancing exercise capacity and/or quality of life in this trial, this would identify a readily implementable, inexpensive therapy for this condition.

Risk/benefit ratio: the results of this study may ultimately lead to an effective treatment for persistent symptoms of AS after AV. Since there is minimal risk and potential benefits to medical knowledge and society, the risk / benefit ratio is acceptable.

11.2. Risks to study subjects

The conduct of these studies will involve 22 human subjects, each exposed to both the active drug (potassium nitrate) and control (potassium chloride) intervention (cross-over design), and therefore studied as their own controls. All subjects will be adults able to give informed consent. Participants will be recruited from the Hospital of the University of Pennsylvania. The ethnic distribution of the population in our center will favor adequate representation of minorities (particularly, African-Americans) in the sample.

The study involves various tests (arterial tonometry, Doppler echocardiography, a cardiopulmonary exercise stress, blood draws) and the administration of randomized therapy (KNO_3 vs. control).

11.2.1. Potential Risks of study intervention (potassium nitrate)

The main potential risks of nitrate administration are related to its potential effect on (1) blood pressure; and (2) methemoglobin levels.

Effects on blood pressure: Regarding the blood pressure reduction, as described above, many studies have demonstrated a reduction in blood pressure in both hypertensive and normal subjects following nitrate supplementation. This was summarized in a recent meta-analysis, demonstrating an approximate 4 mm Hg reduction in systolic blood pressure and 1 mm Hg reduction in diastolic blood pressure.⁽⁴³⁾ Importantly, in a study by our group of a single dose of inorganic nitrate in subjects with HFpEF, we did not observe any change in blood pressure following nitrate ingestion. Importantly, the lack of a blood pressure response to nitrate has been shown in both elderly⁽¹²⁵⁾ and diabetic individuals,⁽¹²⁶⁾ suggesting that there may be important differences in nitrate effect by subgroups. In our pharmacokinetics study, we found a mild (~12 mm Hg) asymptomatic reduction in blood pressure recorded at the time of our study visits during 2-week drug administration, which occurred in the absence of any hypotensive symptoms.⁽¹²⁷⁾ We did not find a reduction in ambulatory blood pressure. Therefore, although we do not anticipate major changes in BP or significant hypotension with this dose, we will implement exclusion criteria and safety blood pressure checks throughout the conduct of the study to ensure subject safety (see next section).

Impact of NO₃⁻ on methemoglobin levels: Nitrate supplementation increases serum nitrite levels through the actions of an enterosalivary circuit and reduction of nitrate to nitrite by anaerobic bacteria in the oral cavity.^(20,25-28) Methemoglobin is generated by the reaction of nitrite with hemoglobin. According to Toxnet, doses between 2-9 grams of NO_3^{-} have been associated with methemoglobinemia. The dose we will use in our study (18 mmol KNO₃) will provide only 1.11 grams (18 mmol $NO_3^- x$ 62 grams/mol $NO_3^- x$ 1mol/1000 mmol), which is well below this threshold. Moreover, this level of nitrate supplementation provides less inorganic nitrate than that found in a traditional Japanese diet, which is rich in vegetables (traditional Japanese diet provides 18.8 mg/kg of nitrate per day x 70 kg individual = 1.3 grams of nitrate).⁽¹²⁸⁾ Moreover, not a single cases of methemoglobinemia was observed in our pharmacokinetics trial, at the same doses used in this trial and in the same patient population. In the pharmacokinetics study we measured methemoglobin every half hour after the first administration as well as during steady-state continued oral administration at doses of both 12 mmol/d and 18 mmol/d and did not find any clinically-significant elevations in methemoglobin. We don't anticipate any significant issues with methemoglobinemia in this study since this is a problem that has been reported with nitrite, but not with nitrate at the doses used in this study.

Safety data:

In a double-blind randomized controlled trial in HFPEF, in which 12.9 mmol of inorganic were administered to patients with HFpEF, efficacy was demonstrated for the study endpoint (please refer to research plan). In this pilot study, no side effects were noted in any subject, except for pink urine (which was not different between the nitrate-rich and nitrate-poor beetroot juice,

because this is a consequence of other components of beetroot juice). As the body is able to reduce oxidized Fe³⁺ in methemoglobin back to Fe²⁺ at a rate of approximately 15% per hour,⁽¹²⁹⁾ the gradual increase in nitrite that occurs after nitrate administration (and the consequent formation of methemoglobin), should occur slowly enough to prevent significant rises in methemoglobin. To the best of our knowledge, methemoglobinemia has not been reported with oral nitrate administration. In our pharmacokinetic study, we did not observe any clinically-relevant elevations in methemoglobin levels⁽¹²⁷⁾.

Other potential safety considerations:

There has been concern regarding whether a high nitrate diet may predispose to gastric cancer in humans through conversion to nitrite in the stomach or through increased urinary excretion of nitrate metabolites. This is a controversial issue derived from animal studies⁽¹³⁰⁾, although the relationship between nitrate intake and cancer has not been demonstrated in humans.^(23,131,132) In fact, many studies show either no relationship or even an inverse relationship between a high intake of nitrate and the occurrence of gastric cancer.^(133,134) (135,136) (137,138) The Joint FAO/WHO Expert Committee on Food reviewed all the available evidence, but failed to establish a definite link between nitrate intake and risk of developing cancer.^(139,140) Furthermore, The World Cancer Research Fund/American Institute of Cancer Research found no evidence linking ingestion of vegetables which are known to be high in nitrate with the development of cancer⁽¹⁴¹⁾. We note that the highly controversial concern regarding cancer risk associated with nitrate intake is related to long-term intake and not a significant issue with our 6-week administration scheme of potassium nitrate.

11.2.2. Potential Risks of study procedures

Potential risks are associated with the study tests, the study interventions (potassium nitrate) and potential breaches in confidentiality.

Cardiopulmonary stress test

This test is used extensively for research purposes with minimal risk to subjects. The most significant risks of the test are dysrhythmias or other cardiovascular complications, which are extremely rare. These procedures will be performed by gualified personnel according to established American Heart Association Guidelines.^(142,143) Non-revascularized myocardial ischemia, which may increase the risk of complications during exercise testing, is an exclusion criterion for the study. We note that prior studies in HFpEF also enrolled subjects with atrial fibrillation⁽¹⁴⁴⁾ and that rate-controlled atrial fibrillation is not a contraindication to exercise testing.

Subjects may feel uncomfortable as a result of pushing themselves during the maximal effort exercise test. Subjects will likely feel short of breath and fatigued as a result of the exercise test. Various other complaints, such as nausea, lightheadedness, and other aches and pains are also possible as a result of the maximal effort exercise study. Although exercise testing may result in exhaustion, rarely do people develop abnormal HR or heart complications during exercise tests. The risk of this happening is the same as if the participant would exert themselves during stressful situations or during exercise elsewhere.

We will perform EKG, HR, and blood pressures monitoring during our exercise test. In addition to the blood pressure (generally increases) and heart rate (generally increases) changes during PULSE AS V3 - 02-Aug-2018 30

exercise, we will also monitor arterial saturation. This will be done non-invasively using a pulse oximeter. Of note, oxygen levels can decrease with exercise, even in individuals without significant cardiopulmonary disease.^(145,146) If the arterial saturation falls to below 88% ("severe exercise induced hypoxemia"⁽¹⁴⁶⁾), we will alert the care provider as this may prompt consideration for additional/alternative causes for arterial hypoxemia.

Venipuncture and IV placement

According to the 2010 WHO guidelines on phlebotomy, major risks associated with blood donations include hematoma at the site of venipuncture in 2-3%, and vasovagal reactions and fainting in 1%. The placement of an intravenous catheter would be anticipated to increase the risk of hematoma and discomfort slightly. Given that the catheter will be in place for a short-period of time, infection is an unlikely complication. Of note, the amount of blood to be drawn in the study is less than the amount of blood drawn at routine blood donation where the risk of syncope of 1% was defined.

Arterial tonometry and assessments of oscillometric arterial pressure waveforms are non-invasive procedures and do not have any known risks.

During various procedures (echocardiography, arterial tonometry), we will use adhesive electrodes attached to the participant's skin to record the electrical signal from the heart. These may occasionally cause skin itching and irritation.

Pregnancy Risks

We will not be enrolling subjects who are pregnant in this study. Right now, there is not enough research on the potassium nitrate to determine the safety of the mother or unborn child. A pregnancy test will be given to women of child-bearing potential prior to enrollment in the study and administration of the supplement. The pregnancy test will be repeated at the 6-week visit (prior to initiation of the second treatment period). If a woman is enrolled of child-bearing potential, we will ask that they use a medically accepted method of birth control (such as an IUD, birth control combination pill, patch, ring, progestin-only pills, Depo Provera Shot, Implanon, complete abstinence, or condoms) while they participate in the study. In addition, we will test for pregnancy at each study visit and discontinue subjects from the study immediately if she becomes pregnant. As subjects with AS are generally older (>55 years old) we do not anticipate this concern to occur with our study population. We will not enroll pregnant women or women who are lactating.

As with any clinical research study, there is a potential for **breach of confidentiality**. Adequate measures will be taken to minimize this risk (below).

11.3. Adequacy of Protection Against Risks

11.3.1. Recruitment and Informed Consent

Written informed consent will be obtained from the subjects by the investigators prior to entry into the research study. This will be performed in accordance with the guidelines and under the supervision of the University of Pennsylvania Institutional Review Boards. The study procedures and interventions and the associated risks will be explained to the subjects during the informed consent process. Only IRB-approved consent forms and related materials will be used.

11.3.2. Protection against risks associated with cardiopulmonary exercise tests

These tests will be performed by qualified personnel according to established American Heart Association Guidelines(142), under ECG monitoring. Personnel with adequate cardiopulmonary resuscitation training and resuscitation equipment (crash cart) will be available during these tests. Similarly, these tests will be performed in a hospital setting where a full code team can be deployed immediately should complications occur.

11.3.3. Protection against risks of potassium nitrate administration:

Subjects will be thoroughly advised regarding the potential risks of the study medication and precautions needed during its administration. We will exclude individuals who are taking sildenafil (Viagra®), tadalafil (Cialis®), or vardenafil (Levitra®) and we will instruct them not to take these medications while participating in the study, since it is likely that these medications may exaggerate the vasoactive effects of potassium nitrate. Similarly, the use of organic nitrate will be contraindicated during participation in this trial.

Supine and orthostatic blood pressure measurements: Supine vital signs will be measured at the screening visit. The subject will rest in a supine position for a minimum of 3 minutes prior to obtaining vital sign measurements. Subjects with a supine systolic blood pressure >110 will be enrolled in the study. The subject will then assume a standing position for 3-5 minutes. Vital signs (BP and pulse rate) will then be measured while the subject is standing. A reduction in systolic blood pressure >20 mmHg will be considered an exclusion criterion for the study. Blood pressure measurements will be repeated after 4 ± 1 weeks of randomized therapy. Measurements will also be prompted by reports of any report of orthostatic symptom by study subjects at any point during the trial. The presence of symptomatic orthostatic hypotension (20 mmHg reduction in systolic blood pressure with associated symptom such as dizziness) will prompt exclusion of patients from the trial.

Safety Clinical Laboratory Tests: Laboratory evaluations will be collected prior to study drug initiation. Among women who are not surgically sterilized or post-menopausal, a urine pregnancy test will be performed at screening (prior to all baseline studies and drug initiation), at the end of the first treatment phase (prior to the initiation of the second treatment phase). Methemoglobin levels will be measured before initiation of randomized therapy and 4 ± 1 weeks after initiation of randomized therapy in both treatment phases (1 and 2). Methemoglobinemia (methemoglobin levels >10%) will prompt discontinuation of patients from the trial. Other tests, including a complete blood count, liver enzymes, a basic metabolic panel (including serum creatinine for assessments of renal function) will also be performed prior to randomization and 4 ± 1 weeks after initiation of randomized therapy.

Significant methemoglobinemia was not observed in our pharmacokinetics trial thus far, at the same doses used in this trial, in a similar patient population. In this study we are measuring methemoglobin every half hour after the first administration as well as during steady-state continued oral administration at doses of both 12 mmol/d and 18 mmol/d. We don't anticipate any significant issues with methemoglobinemia since this is a problem that has been reported with nitrite, but not with nitrate at the doses used in this study. However, a more strict monitoring approach for methemoglobinemia will be implementing should the results of our ongoing pharmacokinetics/safety study raise any concerns.

Side Effect management Plan: No side effects have been observed in our single-dose study or our pharmacokinetics study (in particular, no hypotension or methemoglobinemia). However, a plan for management of side effects will be in place. The use of acetaminophen may be used for headaches during the study. Although hypotension is not expected, it should be managed as per standard clinical practice. In the unlikely event that methemoglobinemia does occur during the trial, we will manage according to best clinical standards.(147) As the endogenous rate of reconversion from methemoglobin to hemoglobin is approximately 15% per hour, most asymptomatic patients can be managed conservatively. Generally, methemoglobin levels >20% with symptoms, or >30% without symptoms, warrant therapy; any patient with levels that are elevated to this range will be referred to the emergency room for management.(147)

11.3.4. Measures to minimize the risk of breach in confidentiality:

All records will be treated with strict confidentiality according to HIPAA guidelines (all study personnel are trained on HIPAA regulations). Blood samples obtained from subjects will be used only for research purposes. Records will be treated with strict confidentiality and stored in a secured, limited access area. A randomly assigned number rather than name will identify all collected samples. A secure database of patient information will be maintained. The investigators and the sponsor will have access to research information and will follow IRB and institutional HIPAA guidelines. Paper files will be saved under lock in a secure IRB-approved area.

11.3.6 Other measures to minimize risk:

Phlebotomy, arterial tonometry, and Doppler echocardiographic examinations will only be performed by appropriately trained personnel as per our institutional standards.

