4.3. Study Population

Subjects will be identified from clinic visits at the University of Pennsylvania for post-TAVR follow up. We will enroll 22 subjects meeting the following criteria:

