4.3.2. Exclusion Criteria

- Supine systolic blood pressure (SBP) < 100 mmHg OR supine diastolic blood pressure (DBP) <60 mmHg
- 2. Poorly controlled hypertension, as defined as SBP > 160 mmHg OR DBP > 100 mmHg
- 3. Pregnancy. Women of childbearing potential will undergo a pregnancy test during the screening visit
- 4. Atrial fibrillation within the prior 8 weeks before enrollment
- 5. Inability/unwillingness to exercise
- 6. Moderate or greater mitral regurgitation or aortic/perivalvular regurgitation, any degree of mitral stenosis, severe right-sided valvular disease, or presence of a mitral prosthetic valve.
- Moderate or severe patient prosthesis mismatch, as defined by Effective Orifice Area Index < 0.85 cm²/m²
- 8. Hypertrophic, infiltrative, or inflammatory cardiomyopathy
- 9. Pericardial disease
- 10. Current angina
- 11. Acute coronary syndrome or coronary intervention within the past 2 months
- 12. Primary pulmonary arteriopathy
- 13. Clinically significant lung disease as defined by: Chronic Obstructive pulmonary disease meeting Stage III or greater GOLD criteria, treatment with oral steroids within the past 6 months for an exacerbation of obstructive lung disease, or the use of daytime supplemental oxygen
- 14. Ischemia on stress testing without subsequent revascularization (during the screening visit)
- 15. Treatment with phosphodiesterase inhibitors that cannot be withheld
- 16. Treatment with organic nitrates
- 17. Significant liver disease impacting synthetic function or volume control (ALT/AST > 3x ULN, Albumin <3.0 g/dL)
- 18. eGFR < 30 mL/min/1.73 m²
- 19. G6PD deficiency. For males of African, Asian or Mediterranean decent, this will be evaluated prior to drug administration. A qualitative test positive for deficiency or a quantitative test with clinically significant G6PD deficiency (<60% of normal activity) will prompt exclusion from the trial (prior to drug administration).
- 20. History of methemoglobinemia or methemoglobin level >5% at baseline visit
- 21. Serum K>5.0 mEq/L
- 22. Severe right ventricular dysfunction.
- 23. Any medical condition that, in the opinion of the investigator, will interfere with the safe completion of the study.
- 4.3.3. Criteria that will prompt exclusion from the trial at the phase 1 visit
- 1. Acute coronary syndrome or coronary intervention for unstable coronary disease after enrollment
- 2. New onset ischemia on stress testing since the time of enrollment

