5.1. Initial Visit

During the baseline study visit, inclusion and exclusion criteria will be reviewed to ensure subject suitability. After eligibility has been confirmed, written informed consent will be obtained from the subject using Institutional Review Board (IRB)-approved documents. Informed consent will be

obtained before any study procedures. Subjects will be given the opportunity to have all questions regarding their participation answered in detail in a private setting before entering the study.

Following informed consent, a physical examination, with measurement of orthostatic blood pressures, will be performed. A urine pregnancy test will be performed in women with childbearing potential. Blood will be collected for measurement of (a) comprehensive metabolic panel; (b) complete blood count; (d) methemoglobin. A pregnancy test (for women of childbearing potential) and Glucose-6-phosphate dehydrogenase (G6PD) deficiency screening (for males of males of African, Asian or Mediterranean decent) will be performed as needed. Blood, urine, and saliva samples will be collected and frozen for nitrate/nitrite and biomarker level determination. The Kansas City Cardiomyopathy Questionnaire (KCCQ) will be administered. Subjects will also be given an informational brochure regarding foods that are high in nitrate/nitrite and thus should be avoided during the study.

Echocardiography will then be performed using a standardized protocol. Images will be obtained from the parasternal long axis, short axis, apical 5-, 4-, 3-, and 2-chamber, subcostal, and suprasternal views for offline analysis of myocardial strain. Dedicated ventricular chamber images will be obtained in the 4- and 2-chamber apical positions for determination of left ventricular volumes. Mitral inflow velocities, including color M-mode interrogation, will be assessed in the 4- chamber view. Tissue Doppler imaging will be performed at the mitral septal position, approximately 1-cm apical to the mitral valve plane. Additional images will be obtained in the parasternal short axis at the level of the papillary muscles, 2-chamber, and 4 chamber apical views for assessment of myocardial strain. Pulse-wave Doppler interrogation of the left ventricular outflow tract (LVOT) will be performed in the apical 5-chamber view.

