5.2. Randomization procedure

A blocked randomization will be performed. Each block will contain an equal number of allocations to KNO₃ followed by KCI versus KCI followed by KNO₃. The order of treatment sequences within each block will be randomized.

5.3. Intervention Phase 1

Subjects will be randomized to receive either active drug (KNO₃) or control (KCI) as the "first" drug for phase A. The initial dose will be one 6 mmol capsule administered twice daily, to be taken with meals. We will provide subjects with a 14-day supply of study medication to account for potential delays in receiving the 2nd batch of medication (i.e., after the 1-week call).

1-week call: Subjects will be called by telephone ~1 week later to assess if they are experiencing any side-effects. Subjects will receive reinforcement of the dietary restrictions imposed during the study. Subjects will be interrogated about headaches and dizziness. If these symptoms are not present, or are not worse compared to the subject's baseline, the drug dose will be up titrated to 18 mmol daily (One 6-mmol capsule taken 3 times per day). The presence of orthostatic symptoms (i.e. sustained lightheadedness upon standing) will prompt a visit to assess for orthostatic vital signs. The presence of symptomatic orthostatic hypotension (20 mmHg reduction in systolic blood pressure with associated symptoms such as dizziness) measured at this subsequent assessment visit will prompt exclusion of patients from the trial.

For subjects who have a serum K at the initial visit between 4.7 and 5.0 mEq/L in the presence of either: (a) potassium-sparing diuretic use, or (b) Estimated glomerular filtration rate of 30-39 mL/min/1.73m2, we will check a serum potassium 1 week after the implementation of the 18 mmol/d dose as a safety measure. A serum potassium > 5.5 mEq/L will prompt exclusion at this point.

At 3 weeks into each interventional phase, the Actigraph devices will be mailed to the subjects. The goal will be for the subjects to wear this device on their wrist during the final week of each interventional phase to look for differences with each therapy. The devices will be brought back by the subject at the endpoint visit.

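### Sections 4.3.2 and 11.3.3 give different blood pressure limits for entry, and the standing-fall exclusion is missing from the exclusion list

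*Combined protocol and SAP*

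**What the plan says.** Section 4.3 introduces the eligibility lists with "We will enroll 22 subjects meeting the following criteria". Two items in Section 4.3.2 set blood pressure limits. Item 1 excludes "Supine systolic blood pressure (SBP) < 100 mmHg OR supine diastolic blood pressure (DBP) <60 mmHg". Item 2 excludes "Poorly controlled hypertension, as defined as SBP > 160 mmHg OR DBP > 100 mmHg". No inclusion criterion in Section 4.3.1 and no exclusion criterion in Section 4.3.2 is orthostatic.

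Section 11.3.3 describes supine and standing measurements at the screening visit. On the supine value it says "Subjects with a supine systolic blood pressure >110 will be enrolled in the study". On the change after standing it says "A reduction in systolic blood pressure >20 mmHg will be considered an exclusion criterion for the study". No symptoms are required for that exclusion.

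Section 5.1 provides the measurement but no limit: "Following informed consent, a physical examination, with measurement of orthostatic blood pressures, will be performed".

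**The concern.** Section 11.2.1 deals with the blood-pressure-lowering effect of nitrate by pointing forward to exclusion criteria and blood pressure checks. The text that supplies them is Section 11.3.3. The stricter entry limits stated there do not appear in the list from which patients are enrolled.

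Staff who screen from Section 4.3.2 alone can enrol a patient whom the safety section would keep out. Whether that patient was correctly enrolled, or is an eligibility deviation, then depends on which section is read. The entry protection described in Section 11.3.3 could also be missed for the patients who start with the lowest pressures or an existing standing fall.

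**Working it through.** The plan states no figure to reproduce, so the check sets the rules side by side.

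| Section | When it applies | Rule |
|---|---|---|
| 4.3.2, item 1 | Entry | Exclude supine systolic < 100 or diastolic < 60 mmHg |
| 4.3.2, item 2 | Entry | Exclude systolic > 160 or diastolic > 100 mmHg |
| 11.3.3 | Screening visit | Enrol at supine systolic > 110 mmHg |
| 11.3.3 | Screening visit | Exclude a standing systolic fall > 20 mmHg, with or without symptoms |
| 5.1 | Initial visit | Orthostatic pressures measured, no limit given |
| 5.3 and 5.5 | On treatment | Exclude a 20 mmHg fall with symptoms |
| 4.3.3 | Phase 1 visit | Supine systolic < 90 mmHg leads to reassessment |

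**Supine limit.** Section 4.3.2 admits 100 mmHg and above; Section 11.3.3 enrols above 110 mmHg. They disagree from 100 to 110 inclusive: 110 − 100 + 1 = 11 whole-mmHg values.

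**Standing fall.** The criterion is in Section 11.3.3 and in 0 of the 23 items of Section 4.3.2. A patient with supine systolic pressure above 110 and up to 160 mmHg, no other exclusion, and an asymptomatic fall above 20 mmHg passes Section 4.3.2 and fails Section 11.3.3.

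**Whether later rules close the gap.**
- The one-week call leads to an orthostatic check only if the patient reports symptoms, and removal requires "The presence of symptomatic orthostatic hypotension (20 mmHg reduction in systolic blood pressure with associated symptoms such as dizziness) measured at this subsequent assessment visit". An asymptomatic fall present at screening is not caught.
- Section 4.3.3 acts after the first treatment phase, and at 90 mmHg. It neither sets nor reconciles the entry limit.

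**Illustration of what the 10 mmHg difference could mean.** Section 11.2.1 reports three results: no change after a single dose, a systolic reduction of about 4 mmHg in a meta-analysis, and an asymptomatic reduction of about 12 mmHg at study visits in the pharmacokinetics study. Assume these transfer to post-AVR patients and that the 12 mmHg is systolic, which the text does not say. A patient entering at 100 mmHg would then reach:
- 100 − 0 = 100 mmHg;
- 100 − 4 = 96 mmHg;
- 100 − 12 = 88 mmHg, below the protocol's own 90 mmHg reassessment limit.

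A patient entering above 110 mmHg would stay above 110 − 12 = 98 mmHg. The same section found no fall in ambulatory pressure, so this shows a range and is not a forecast.

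**The case against.** The strongest reply is that the two sections can be applied together: enrol above 110 mmHg with no standing fall above 20 mmHg. Section 11.3.3 expressly makes the fall an exclusion for the study, and Section 4.3.2 is silent on it rather than contrary. The protocol also puts other screening exclusions outside Section 4.3.2: desaturation on the walk test (Section 5.1) and lactation (Section 11.2.2). On this view the orthostatic half is a missing cross-reference. That is a fair description of that half. It does not help with the supine limit, where two different numbers are attached to one measurement.

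The 110 mmHg sentence is also loosely worded. It says who will be enrolled, not who will be refused, and read literally it would admit patients whom item 2 excludes for high pressure. Treating it as a lower limit is an inference, though the natural one for a screening threshold in a safety section.

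Other safeguards exist. Item 23 of Section 4.3.2 allows exclusion on the investigator's judgement. Dosing starts at 12 mmol per day and rises to 18 only if headache and dizziness are absent or no worse than at baseline. Orthostatic pressures are repeated at both endpoint visits and whenever orthostatic symptoms are reported. These reduce the risk, but none supplies an entry threshold, and the on-treatment orthostatic exclusion needs symptoms.

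Finally, the screening forms are not in the documents and may already carry the stricter limits. That is possible, but the protocol should not depend on it.

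**Conclusion.** The concern holds. The protocol has two lower limits for supine systolic pressure at entry, 100 and 110 mmHg, and an orthostatic exclusion that is absent from its exclusion list. No text says which section governs. The supine disagreement covers 11 whole-mmHg values.

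How many of the 22 patients this could affect cannot be computed, because the documents give no distribution of supine pressure or standing falls after valve replacement. The conclusion assumes that the 110 mmHg sentence is meant as a lower limit; the omission of the standing-fall rule from Section 4.3.2 does not depend on that reading.

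The consequence is for safety and for the definition of eligibility. Sample size and power are unchanged, and the treatment comparison is not biased by this alone. The correction should be made, because Section 11.2.1 relies on these limits and the change is small.

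**What to change.** 1. Choose one supine limit. Either change item 1 of Section 4.3.2 to exclude supine systolic pressure of 110 mmHg or less, keeping the diastolic limit of 60 mmHg, or, if the clinical team intends 100 mmHg, correct Section 11.3.3 to match. The documents do not show which was intended, so the sponsor must decide.
2. Add a standing systolic fall above 20 mmHg at screening, with or without symptoms, to the exclusion list in Section 4.3.2.
3. Have Section 11.3.3 refer to Section 4.3.2 for the entry limits, so that they are stated once.
4. Check the screening checklist against the amended list and update it where needed.

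The cost is a protocol amendment and, if needed, a revised checklist. No procedure is added, because orthostatic pressures are already taken at the initial visit. Appendix 1 places randomization after the baseline laboratory results are available, so the standing-fall result can be applied before a patient is randomized. Recruitment would be slightly slower if the 110 mmHg limit is kept.
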